#### **Sample collection comparison**

All samples will be analysed in duplicate and the results averaged. Passing-Bablok regression and Pearson correlation coefficient will be used to compare and assess correlation of the results of venous and capillary samples. Bland-Altman analysis will assess agreement and determine presence of any bias between the results obtained from venous and capillary sample collection. 95% confidence intervals will be calculated. Statistical analysis will be performed using the Analyse-It add-in for Microsoft Excel.

Stability: Samples will be analysed in duplicate and the results averaged. Means of each group will be

calculated and compared to baseline. Differences of  $\pm 15\%$  will be deemed acceptable.

**Effect of haematocrit concentration:** The 4 samples will be analysed in duplicate and the results averaged. Differences of 15% will be deemed acceptable and this would confirm samples collected using Mitra® devices are unaffected by differing haematocrit concentrations.

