**Background (*Literature review*):**

Tacrolimus is an immunosuppressant which acts by inhibition of calcineurin. It's typically used as a first line drug to prevent allograft rejection in renal transplant patients (1). With pharmacokinetic variability between patients and a narrow therapeutic range, therapeutic drug monitoring (TDM) is essential to support graft survival. Low levels of tacrolimus risk organ rejection, whilst toxic levels risk nephrotoxicity and other adverse effects including neurotoxicity, electrolyte disturbances and hyperglycaemia (2). Clinical guidelines suggest target tacrolimus ranges, but levels are determined by renal clinicians and are patient specific, depending on individual circumstances, as well as the time since transplantation (3).

Renal transplant patients require lifelong monitoring of immunosuppressant levels and renal function to assess graft kidney stability. Renal function is monitored by measuring serum creatinine and urine protein excretion, levels of which determine the need to perform a biopsy if graft dysfunction is suspected (3). Creatinine is the product of creatine phosphate catabolism in muscle. Its endogenous production at a constant rate and clearance by glomerular filtration makes it a useful marker of graft function, with increasing levels indicating a reduced glomerular filtration rate and thus some element of renal disease (4). Creatinine is measured enzymatically on the Roche platform, as part of a urea and electrolyte panel.

The Renal department is currently managing just under 1000 patients with a functioning kidney transplant, with this number increasing annually. There are 80-100 transplants per year and a current waitlist of just under 300 patients. Following successful transplantation, every patient requires lifelong monitoring of transplant function. This is not only a long-term commitment for these patients, but also the renal department in providing the aftercare. Current practice for post-transplant monitoring involves regular venepuncture to collect a venous blood sample for tacrolimus measurement and a 'dialysis profile' (urea and electrolytes, bicarbonate, CRP). Clinical guidelines recommend monitoring tacrolimus levels by trough sample 3 times a week initially. Frequency decreases over time to every 4-6 weeks at 6-12 months and then every 3-6 months at 12 months post-transplant, unless adjustments are made to the dosage which warrants more frequent

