#### **Objectives and Specific Aims:**

- To develop and validate an LC-MS/MS method for tacrolimus and creatinine measurement in adult renal transplant patients.

- To compare tacrolimus and creatinine concentrations in venous samples collected by venepuncture and capillary samples collected using Mitra® devices.
- To implement home blood sample collection into routine clinical practice for renal transplant patients.
- To publish the study findings to encourage uptake of remote blood sample collection using VAMS® technology.

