## **Methodology**

### **Sample collection**

Patients attending blood clinic for routine venepuncture will also have a finger prick and 10 $\mu$ l blood will be collected using the Mitra® device (Neoteryx), according to manufacturer's instructions. The usual venous EDTA and serum samples will be collected by venepuncture by trained phlebotomists/nurses. Tacrolimus and creatinine are measured in venous blood samples (whole blood and serum, respectively) as part of routine patient care therefore these will be processed as normal, and results reported. The paired capillary samples collected using the Mitra® device will be batched and run when appropriate on the LC-MS/MS. Mitra® devices will be stored at -20°C prior to analysis. Any incorrectly filled Mitra® devices (over or under filled) which would affect sample quality will be rejected.

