### **Creatinine method evaluation**

Method comparison will be performed by comparing creatinine results obtained by enzymatic assay on the Roche platform with results obtained by LC-MS/MS. A minimum of 50 patient samples will be analysed, as well as EQA samples. Within and between batch precision will be performed by loading Mitra® devices with IQC sample. 3 levels of IQC will be run a minimum of 5 times within the same analytical run and between analytical runs, on different days. Precision studies will be used to determine the LLOQ. Low patient pools will be prepared to give appropriate concentrations. Samples will be analysed 10 times within the same analytical run and 10 times between runs.

Linearity will be determined by performing dilutions of the creatinine standard material to prepare an extended standard curve. To assess recovery, blank samples will undergo sample preparation steps and will be spiked with the 3 different levels of creatinine QC. Carryover will be assessed by analysing an alternating high creatinine concentration sample with repeated analysis of a low creatinine or blank sample.

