#### **Creatinine method evaluation**

Precision: The following statistics will be calculated for within and between batch precision: mean, SD and %CV. A CV less than 20% will be deemed acceptable.

Accuracy: All samples will be analysed in duplicate and the results averaged. Passing-Bablok regression and Pearson correlation coefficient will be used to compare and assess correlation of the results obtained from each method. Bland-Altman analysis will assess agreement and determine presence of any bias between the results obtained from the different methods. 95% confidence intervals will be calculated. Statistical analysis will be performed using the Analyse-It add-in for Microsoft Excel.

Linearity: The diluted creatinine standards will be analysed in duplicate and plotted against the concentration to give the  $r^2$  value. Means should be within 15% of each other to confirm linearity.

LLOQ: Mean, SD and %CV will be calculated. LLOQ will be defined as the level with a between batch precision of <15%.

Recovery: Each level of QC will be run in triplicate and the average calculated, with the recovery being expressed as a percentage with an acceptability of 100±20%.

Carryover: The % carryover from high to low concentrations will be determined. Differences of ±15% will be deemed acceptable.

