**Definition of the end of study:**

The trial will end once enough samples have been collected to cover the required range of tacrolimus and creatinine concentrations for the assay. This will be a minimum of 50 samples. Only a single sample is required from each patient and there will be no follow up of the same patient. Patients will continue to be monitored post-transplant and have blood samples taken throughout the time of the study as part of the routine care, but they will not be included in the study.

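### Bland-Altman limits computed on averaged duplicates will be too narrow for one capillary against one venous result, if routine samples are measured once; single-result limits should be reported as well

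*Protocol*

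**What the plan says.** Under Data Analysis, Sample collection comparison, the protocol fixes the handling of replicates for both collection methods: "All samples will be analysed in duplicate and the results averaged". It then says that "Bland-Altman analysis will assess agreement and determine presence of any bias between the results obtained from venous and capillary sample collection". Agreement is thus named as a purpose alongside bias, and 95% confidence intervals are planned.

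The level at which the duplicate is taken (a second collection, a second extraction or a second measurement) is not given. Two places bear on it. Methodology, Sample collection, says "Patients attending blood clinic for routine venepuncture will also have a finger prick", with 10 µl collected on the Mitra device. Definition of the end of study says "Only a single sample is required from each patient and there will be no follow up of the same patient". Together they suggest, without settling it, that capillary duplicates are repeat measurements of one collection.

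The number of measurements behind a routine result is not stated for either method; routine venous samples are only said to be handled in the usual way. Imprecision is studied separately for creatinine: "Within and between batch precision will be performed by loading Mitra® devices with IQC sample", and "A CV less than 20% will be deemed acceptable". That CV is not carried into the limits of agreement, and no counterpart for capillary tacrolimus is stated.

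**The concern.** Averaging two replicates removes half of the replicate variance from each method before the differences are formed. The spread of those differences, and hence the limits of agreement, then applies to a pair of averages. A clinician who receives one capillary measurement is in a different position.

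This matters because of the intended use. One stated objective is "To implement home blood sample collection into routine clinical practice for renal transplant patients", where a patient's result is read on its own, and the Background says of tacrolimus: "With pharmacokinetic variability between patients and a narrow therapeutic range, therapeutic drug monitoring (TDM) is essential to support graft survival". Limits that belong to averages would make the two collection methods look somewhat more interchangeable for one patient than they are. The error can go only one way, in favour of the device, and it does not shrink as more samples are collected.

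**Working it through.** The protocol gives no limits of agreement, SD or sample-size calculation, so there is no figure to reproduce.

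**Inputs from the protocol.** Two replicates per sample, averaged; at least 50 pairs; one sample per patient. The only bound on imprecision is the creatinine CV below 20%.

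**Assumed inputs (not in the protocol).** Pair-specific scatter s_pair of 5% or 10%; capillary and venous CVs (s_c, s_v) of 10% and 5%, or 7% and 4%. The part of each CV that the duplicate actually replicates is r_c and r_v. Cases are written s_pair/s_c/s_v.

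**Formulas.**
- Var(single) = s_pair² + s_c² + s_v²
- Var(averaged) = Var(single) − 0.5·r_c² − 0.5·r_v²
- Limits = bias ± 1.96·SD
- Narrowing = 1 − SD(averaged)/SD(single)
- Coverage of single-result differences by the averaged limits = 2Φ(1.96·SD(averaged)/SD(single)) − 1

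**Duplicates as repeat measurements of one collection** (r_c = r_v = r, scatter 5%):

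| Case | r | Var(single) | Var(averaged) | Limits, averaged vs single | Too narrow by | Coverage |
|---|---|---|---|---|---|---|
| 5/10/5 | 1% | 150 | 149 | ±23.9% vs ±24.0% | 0.3% | 0.949 |
| 5/10/5 | 2% | 150 | 146 | ±23.7% vs ±24.0% | 1.3% | 0.947 |
| 5/10/5 | 3% | 150 | 141 | ±23.3% vs ±24.0% | 3.0% | 0.943 |
| 5/7/4 | 1% | 90 | 89 | ±18.5% vs ±18.6% | 0.6% | 0.949 |
| 5/7/4 | 2% | 90 | 86 | ±18.2% vs ±18.6% | 2.2% | 0.945 |
| 5/7/4 | 3% | 90 | 81 | ±17.6% vs ±18.6% | 5.1% | 0.937 |

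**Duplicates that replicate all measurement error in both methods** (r_c = s_c, r_v = s_v):

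| Case | Var(single) | Var(averaged) | Limits, averaged vs single | Too narrow by |
|---|---|---|---|---|
| 5/10/5 | 150 | 150 − 50 − 12.5 = 87.5 | ±18.3% vs ±24.0% | 23.6% |
| 5/7/4 | 90 | 90 − 24.5 − 8 = 57.5 | ±14.9% vs ±18.6% | 20.1% |
| 10/10/5 | 225 | 225 − 62.5 = 162.5 | ±25.0% vs ±29.4% | 15.0% |
| 10/7/4 | 165 | 165 − 32.5 = 132.5 | ±22.6% vs ±25.2% | 10.4% |

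**Both methods routinely run in duplicate.** The averaged limits are then the right ones and the error is zero.

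**Check of the correction.** The single-result variance can be recovered from the same data by adding back 0.5·s_within² for each method, with s_within estimated from the duplicates. In 20,000 simulated studies of 50 pairs (5/10/5, r = 4%), the true single-result SD was 12.25. The mean estimate was 11.50 from averaged duplicates and 12.18 from the add-back formula (sampling SD 1.10). Using the first replicate only gave 12.17, with a larger sampling SD of 1.23.

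**Sampling error for scale.** With 50 pairs, the 95% confidence interval of an SD runs from √(49/χ²₀.₉₇₅) = 0.84 to √(49/χ²₀.₀₂₅) = 1.25 times the estimate.

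**The case against.** The strongest reply is that the condition is not in the document. Nothing says that a routine result rests on one measurement, and if both methods are run in duplicate in routine use there is nothing to correct. This stands, and the point is therefore conditional.

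Second, no stated decision depends on the limits. The only downstream use given, in Deriving a new reference range, takes the bias, which averaging does not change. No acceptance limit is set for the limits of agreement. This also stands.

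Third, the likely effect is small. If duplicates are repeat measurements with a CV of 1-3%, the narrowing is well inside the sampling error of an SD from 50 pairs. This holds for a single study, but the shift is systematic and remains however many samples are added.

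Fourth, extra Bland-Altman output may be left to an analysis plan or to the departmental protocols that the Data Analysis section cites. That would answer a complaint about missing detail. Here the averaging is written into the protocol for an analysis whose stated purpose includes agreement, and nothing in the protocol adjusts for it.

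A reader might infer that the limits will be understated by a fifth or more, or that the device could be wrongly accepted. The documents support neither. The larger figures require duplicates that repeat every source of measurement error in both methods, whereas the description of one finger prick and one sample per patient points the other way. No acceptance rule exists that the limits could wrongly satisfy.

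**Conclusion.** The concern holds in a conditional form and is of low severity. If routine capillary or venous results are single measurements, the planned limits are too narrow for one capillary result against one venous result, with certainty as to direction whenever replicate error is above zero. The size cannot be determined from the protocol. On the assumed inputs, it is about 0.3-5% for repeat measurements of one collection (repeat CV 1-3%, scatter 5%). It reaches about 10-24% only if duplicates replicate all measurement error in both methods (scatter 5-10%). The reading that best fits the sampling description is the smaller one. Mean bias, the reference-range step and all stated decisions are unaffected.

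**What to change.** Keep averaged duplicates for the bias estimate and for Passing-Bablok regression. In Data Analysis, Sample collection comparison:

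- State the level at which the duplicate is taken: collection, extraction or re-measurement.
- Retain the individual replicate values.
- Also report single-result limits of agreement with 95% confidence intervals (for example by bootstrap over patients), using SD_single² = SD_averaged² + 0.5·s_within,capillary² + 0.5·s_within,venous². Estimate each s_within from the duplicates, on the same absolute or percent scale as the differences.
- Omit the term for any method that will be run in duplicate routinely.
- State that the limits apply to samples collected in clinic, as studied, and do not cover added error from home collection or posting.

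The cost is one formula applied to measurements already planned, with no new samples or procedures. The downside is slightly wider, less favourable limits.

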monitoring. Serum creatinine should be measured at each clinic visit, as well as urine dipstick analysis for urine protein (3). Thus, the frequency of biochemical monitoring depends on patient circumstances, but once a steady state is achieved, the monitoring window increases.

The COVID-19 pandemic put considerable strain on patient care, with limited access to healthcare settings (including phlebotomy services) due to increased infection control measures. Transplant patients are already immunocompromised and often have comorbidities, so it is important to minimise unnecessary exposure to high-risk environments, including hospital settings. When presenting with COVID-19, solid organ transplant patients have an increased 30-day mortality compared to non-transplant patients, and they are also more likely to require mechanical ventilation and critical care (5). Furthermore, COVID-19 has been noted as a causative factor in graft rejection and subsequent loss (6). The risks associated with COVID-19 infection are applicable to various other disease groups, including patients undergoing cancer treatment (7). This highlights a requirement to protect these vulnerable groups in the hope of a more favourable patient outcome. To overcome some of the challenges imposed by COVID-19 and alleviate the associated risks for renal transplant patients, virtual appointments (by telephone or video consultation) were utilised. This enabled patients to attend their appointment anywhere, providing greater flexibility to both the patient and clinician. However, there is little benefit to these virtual appointments if the patient is still required to attend a healthcare setting for blood sample collection. Hence, alternative approaches to blood sample collection were explored.

A promising microsampling device has been growing in popularity. Neoteryx (Torrance, CA 90501, USA) has developed Mitra® devices with VAMS® (volumetric absorptive microsampling) technology. Patients collect a capillary blood sample by finger prick and send it to the laboratory for testing. Studies have shown results correlate well with those obtained from a venous blood sample collected by venepuncture (8, 9). There has been a positive bias noted for capillary tacrolimus concentrations, but this could be overcome by establishing new target ranges for patients (10). This method of sample collection is already being utilised by 2 Trusts within the UK to support transplant monitoring in paediatric patients.

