#### **Rationale and Significance of Study:**

The main advantage of this collection method is that it allows the remote collection of a blood sample. This reduces patient attendance at blood clinics and resultant strains on phlebotomy staff and clinics, eliminates administration requirements for transplant nurses and saves both the patient and the NHS time and money. Of most importance is the great flexibility and convenience this collection device offers, as patients can collect samples at anytime and anywhere, providing greater freedom compared to current procedures.

Patient adherence to immunosuppressants is a key factor in potential graft rejection, with lack of immunosuppression leading to graft loss, even years after transplantation (12). Due to the increased flexibility offered by the Mitra® device, it is anticipated that this collection method will improve patient compliance with TDM. Better timed sample collection is also expected (ie. a 'true' trough sample) as patients are not subject to blood clinic operating hours. Consequently, potentially more frequent and better-timed sample collections will be more clinically useful.

Importantly for patient management, is the ability to calculate AUC (area under the curve). This is not currently possible with current protocols as regular samples would be required which inconveniences the patient. AUC targeted therapeutic monitoring of tacrolimus may be more clinically informative than current pre-dose tacrolimus measurements and be a better indicator of immunosuppressant efficacy (13).

It is also worth noting the current issues encountered with venepuncture for venous blood collection. Increased patient anxiety occurs because of needle phobia (although uncommon) and if the patient is difficult to bleed. The latter of which can result in lengthy appointments whilst the required samples are obtained. In comparison, capillary blood sampling is minimally invasive, and a much smaller volume of blood is required (particularly useful for the elderly). However, a well-known issue associated with capillary blood is the volumetric haematocrit bias and poor blood spot quality, resulting in non-homogenous samples and inaccurate results (14). This issue is alleviated using Mitra® devices because a defined blood volume is collected.

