### **Sample analysis**

Venous EDTA whole blood samples (collected by venepuncture) and capillary whole blood samples (collected by VAMS®) will be analysed for tacrolimus using a validated LC-MS/MS assay in routine clinical use in the lab using the Waters ACQUITY UPLC system and Xevo TQD MS. Additionally, samples from the UK NEQAS immunosuppressants scheme will be analysed as above for tacrolimus. Capillary whole blood samples (collected by VAMS®) and serum samples will be analysed for creatinine using an LC-MS/MS method which will be developed based on a previously published method (11). For the method comparison, serum samples (collected by venepuncture) will be analysed for creatinine using an enzymatic method on the Roche platform. Additionally, samples from the UK NEQAS clinical chemistry scheme will be analysed as above for creatinine. All sample analysis will be performed in an ISO 15189 accredited laboratory.

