### **Sample collection comparison**

To compare results collected by venepuncture and results collected by VAMS® sampling, a minimum of 50 paired patient samples will be analysed for tacrolimus and creatinine by LC/MS-MS. 20 EQA samples from the NEQAS immunosuppressant scheme will be analysed for tacrolimus and 20 EQA samples from the NEQAS clinical chemistry scheme will be analysed for creatinine by LC-MS/MS. To compare creatinine methods (enzymatic and LC-MS/MS), creatinine samples will also be analysed using an enzymatic assay on the Roche platform.

To test the stability of whole blood collected by VAMS®, 5 samples will be stored at varying temperatures for 7, 14 and 21 days. The samples will be stored at -20°C, 4°C, room temperature and

37°C. This will test the effect of temperature extremes which may occur due to postal delivery of the Mitra® devices. The stability of post extraction samples will also be tested by storing the 96 well plate at 4°C post analysis and re-assaying at 24 and 48 hours post extraction. To investigate the effect of different haematocrit concentrations, blood cells and plasma will be mixed 20:80, 40:60, 60:40 and 80:20 to obtain 4 different haematocrit levels (20%, 40%, 60% and 80%).

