#### **Deriving a new reference range**

If the LC-MS/MS tacrolimus and/or creatinine method shows a clinically significant bias compared to current methods, this will be confirmed by obtaining further patient comparison data. If confirmed, the reference range will need to be reviewed and amended accordingly. Any bias identified by Bland-Altman analysis will be used to derive a new reference range for patients being monitoring using blood collected using the Mitra® devices.

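### The haematocrit test names no comparator and has no reference result for each mixture, so a 15% difference cannot confirm that Mitra samples are unaffected by haematocrit

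*Protocol*

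**What the plan says.** The Methodology part of the Protocol (Sample collection comparison) states that "blood cells and plasma will be mixed 20:80, 40:60, 60:40 and 80:20 to obtain 4 different haematocrit levels (20%, 40%, 60% and 80"%). It mentions no spiking to a common concentration, no second measurement of the same mixture, and no analyte.

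The Data Analysis part (Sample collection comparison, Effect of haematocrit concentration) has the four samples run in duplicate and averaged. It then sets both the limit and the inference: "Differences of 15% will be deemed acceptable and this would confirm samples collected using Mitra® devices are unaffected by differing haematocrit concentrations". The 15% has no sign and no stated point of comparison. The stability rule just above it has both: group means are "calculated and compared to baseline", with a limit of plus or minus 15%.

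The Rationale names haematocrit bias as a known problem of capillary blood and says of it: "This issue is alleviated using Mitra® devices because a defined blood volume is collected". The haematocrit test is the only experiment in the plan aimed at that statement.

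**The concern.** Two things are missing, and they matter in different ways.

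First, the comparator. The 40% mixture, the mean of the four, and largest against smallest all fit the text. The same data can pass on one reading and fail on another.

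Second, a reference result. Changing the proportion of cells changes the true whole-blood concentration of any analyte that is not equally distributed between cells and plasma. A difference between mixtures is then part concentration and part device, and the design has nothing to split them. An unaffected device can fail. An affected one can pass if its error runs opposite to the true change. If both run the same way, the rule errs towards failing the device.

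At stake is the support for the Rationale's statement, and through it part of the case for routine use. Later analysis cannot supply a reference result once the mixtures have been used up.

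**Working it through.** **Inputs from the Protocol.** Haematocrit H = 0.2, 0.4, 0.6, 0.8; duplicates; limit 15%. There is no sample size or power figure to reproduce, because the 15% is a bare limit.

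**Assumed inputs.** R (cell:plasma concentration ratio); assay CV of 5% or 10% (the only stated precision limit is a CV below 20%, for creatinine); and an illustrative faulty device whose recovery falls in a straight line by 25% from the 20% to the 80% mixture.

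**Step 1, true concentration.** With plasma set to 1, C(H) = (1 - H) + R·H. At R = 2 this gives 1.2, 1.4, 1.6, 1.8, which is -14%, 0, +14%, +29% against the 40% mixture with a perfect device.

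**Step 2, range of R in which a perfect, noise-free device passes.**
- Against the 40% mixture, the largest deviation is at 80%: 0.4(R - 1)/(0.6 + 0.4R) = ±0.15, so R = 0.31/0.46 = 0.67 to 0.49/0.34 = 1.44.
- Against the mean: 0.3(R - 1)/(0.5 + 0.5R) = ±0.15, so R = 0.225/0.375 = 0.60 to 0.375/0.225 = 1.67.
- Largest against smallest, for R > 1: (0.2 + 0.8R)/(0.8 + 0.2R) = 1.15, so R = 0.72/0.57 = 1.26. For R < 1 the limit is the reciprocal, 0.79.

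**Step 3, the comparator alone (R = 1).** The faulty device reads 1, 0.917, 0.833, 0.75. Against the 40% mixture the worst difference is -18% (fail). Against the mean of 0.875 it is ±14.3% (pass). Largest against smallest it is 33% (fail).

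**Step 4, pass rates with noise.** 400,000 simulated sets of duplicate means (SD = CV/√2), CV 5%. Each cell gives 40% mixture / mean / largest against smallest.

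| R | Unaffected device passes (%) | Device with 25% loss passes (%) |
|---|---|---|
| 0.8 | 89 / 99 / 47 | 0 / 0.3 / 0 |
| 1 | 99 / 100 / 97 | 14 / 40 / 0.1 |
| 1.25 | 83 / 99 / 47 | 81 / 98 / 31 |
| 1.5 | 33 / 72 / 1 | 98 / 100 / 92 |

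At R = 1 and CV 10%, an unaffected device passes 70 / 95 / 50%.

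**Step 5, precision of a ratio-based estimate.** Take q = Mitra/liquid at each level, with both forms at the same CV. The change in q between two levels has SE of about CV·√(4/n) for n replicates per form.
- n = 2, CV 5%: SE = 7.07 points. The 95% half-width is 2.776 × 7.07 = 19.6 points (4 df), or 2.306 × 7.07 = 16.3 points if all eight groups are pooled (8 df). Either exceeds 15.
- n = 6 (20 df, t = 2.086): 8.5 points at CV 5% and 17 points at CV 10%.

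**Step 6, which levels to judge.** If only 80% against 20% is judged (n = 6, CV 5%), a device reading 20% low at both middle levels and correctly at the ends passes 99.97% of the time. Judging all levels against the 20% mixture in the same simulation model lowers that to about 2%; an unaffected device passes 99.9% and the 25% loss 0.1%. At CV 10% the three rates are about 9%, 84% and 5%.

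**The case against.** The strongest reply is that this is laboratory detail. The Data Analysis section refers to published recommendations and to the department's own protocols, which are not shown and may name the comparator or a spiking step. That stands as a limit on the point: nobody can say from this document that the laboratory has no comparator. It does not rescue the text, because the Protocol itself fixes the limit and the conclusion, and that conclusion does not follow from the test it describes.

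A second reply is that R appears nowhere in the documents. At R = 1 and low CV the rule behaves well for an unaffected device, and a wrong pass caused by R needs a device error in the opposite direction. This also stands. The 25% straight-line loss is likewise an illustration.

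A third is that this is a four-sample bench check. True, and participants' haematocrit will be summarised, although no analysis by haematocrit is stated.

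A reader might infer that the test will give the wrong answer, that Mitra is affected by haematocrit, or that the venous-capillary comparison is undermined. The documents support none of these. The first needs a value of R that they do not give, the second is what the experiment is meant to find out, and the third rests on separate paired patient samples.

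**Conclusion.** The point holds in limited form. As written, the rule has no named comparator and no reference result for each mixture, so meeting it does not confirm absence of a haematocrit effect.

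The missing comparator matters even at R = 1, where it alone moves the pass rate of the assumed faulty device between 0.1% and 40%. The missing reference matters only if R differs from 1. By R = 1.25 the rule barely separates the two devices on the first two readings, and at R = 1.5 it favours the faulty one. These sizes depend on the assumed R, CV and shape of loss. The mass-balance argument and the gap in the text do not.

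This should be settled before the mixtures are made. It is not a flaw in the main comparison.

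**What to change.** 1. State which analyte or analytes are tested. For tacrolimus, also assay each mixture as liquid EDTA whole blood. The Protocol says that venous EDTA and capillary samples "will be analysed for tacrolimus using a validated LC-MS/MS assay in routine clinical use in the lab", so no new method is needed. For creatinine the stated matrices are narrower: "Capillary whole blood samples (collected by VAMS®) and serum samples will be analysed for creatinine using an LC-MS/MS method". Use a liquid reference there only after the method is shown to work in liquid whole blood; otherwise draw no haematocrit conclusion for creatinine from this test. An assigned value of endogenous amount plus spike is no substitute unless the endogenous amount is negligible or measured, because it depends on the same unknown R.
2. Form the Mitra/liquid ratio at each level, which cancels R provided the liquid assay itself recovers equally across levels. Compare every level with one named in advance, for example the 20% mixture, and apply ±15% to all of them. A constant capillary bias cancels too. The Background expects one ("There has been a positive bias noted for capillary tacrolimus concentrations, but this could be overcome by establishing new target ranges for patients") and the reference-range section deals with it ("Any bias identified by Bland-Altman analysis will be used to derive a new reference range").
3. Report each change with its 95% confidence interval, and replace the claim of confirmation with that estimate, limited to the levels tested. Set replicates from the measured CV. Duplicates are too few for an interval narrower than the limit even at CV 5%. Six per form give about ±8.5 points at CV 5%, but still about ±17 at CV 10%.

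**Cost.** The plan has 4 × 2 = 8 Mitra assays per analyte. A liquid reference in duplicate adds 8. Six replicates of both forms make 4 × 6 × 2 = 48, so 40 extra. Creatinine also needs a matrix check, and the conclusion becomes less categorical. Naming the comparator and softening the conclusion need no laboratory work.
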